We propose a GLMM to analyze data. One of the main advantages of GLMM is to provide unbiased estimates when there are missing outcomes during the follow up period. For the missing values at the baseline or partial baseline collected data, we will use a multiple imputation approach.¹³¹ Models will also be run on the raw, non-imputed data. Inferences for the trial arm, wave, and interaction between trial arm and wave did not differ between the analyses of the raw and multiply imputed data. Rates of reduction will be calculated from population-averaged rates, which control for all other covariates in the multivariable model. Models will be calculated using R, and model fit will be evaluated by diagnostic statistics and residual plots. Secondary Outcomes: We will use the proposed GLMM to analyze secondary outcomes with appropriate choice of link functions according to the outcomes. All analyses will be done on the final data set (baseline n=900).

C.14.a. Missing data.

Missing data may occur in the proposed study in several ways. First, missing data may occur due to item non-response. When missing data is limited to only a few items on a measure, we will prorate

Table 4. Codes for design variables

Months	Intervention Arm				Delayed Intervention Arm			
	Arm	W	I	FU	Arm	W	I	FU
Baseline	0	0	0	0	1	0	0	0
3 mo	0	1	1	0	1	1	0	0
6 mo	0	2	1	1	1	2	0	0
9 mo	0	3	1	2	1	3	0	0
12 mo	-	-	-	-	1	4	1	0

total scores for a measure by taking an average score on the measure and multiplying it by the total number of items in the scale. Missing data can also occur from attrition due to missed assessments or dropout from the study. Prior to performing any outcome analyses, we will evaluate the amount, reasons, and patterns of missing data. If the reason for missing data is not related to the outcome of interest, then the missing data are considered to be missing completely at random (MCAR) and complete case analysis will still generate unbiased estimates.¹⁰³ We will conduct sensitivity analyses to compare estimates of treatment effects with and without multiple imputation to assess the effect of missing data on statistical inference.

C.15. MyPEEPS Mobile RCT In-depth Interviews

Selected participants will be interviewed about the MyPEEPS Mobile RCT to better understand their overall experience using the MyPEEPS application and the study recruitment process.

Recruitment: For the in-depth interviews, we will recruit up to 40 participants across the four study sites (New York, Chicago, Birmingham, and Seattle), 10 participants from each study site. We anticipate that a total of 40 participants will be an adequate number of participants to reach saturation based on our earlier studies focusing on similar topics.³² Through a purposive sampling we will draw from a group of participants who agreed to be contacted for future studies and completed the MyPEEPS mobile RCT. Participants will be given information about the in-depth interview, the time involved (approximate length of time: 1-1.5 hour), and compensation (\$30). The interview compensation is consistent with payments made in prior studies.

Procedures: All in-depth interviews will be conducted with participants individually and recorded using an online platform (e.g. Zoom). Before the start of the interview, the study staff will first explain the purpose of the project and participants will review and sign a written informed assent/consent in electrotonic form. The informed assent/consent form provides details of the study procedures, risks, benefits, site contact information, and the nature of confidentiality and voluntary participation. The consent process also covers information on the timeline, task involved, and compensation for time. To ensure understandability, the study staff will read the form to the participant and ask them to summarize their understanding of the study procedures. Before a participant signs the informed assent/consent form, staff will answer any questions. Participants will be given a copy of the informed assent/consent form for their records.

Following the completion of the electronic informed assent/consent process, participants will begin the indepth interview. We will ask structured questions pertaining to the participants' overall experience with the MyPEEPS Mobile RCT and the recruitment process, and the relevance or impact of the MyPEEPS application to their lives. During the interview, we will also provide participants with a handout listing the MyPEEPS activities to help with recall. The individual in-depth guide will include the following questions

- 1) Please describe your experience navigating, or moving through, the MyPEEPS app activities and any technical issues.
- 2) What are some changes you think should be made to the MyPEEPS mobile app to make it easier to use? What worked/ did not work? What app activities or topics would you add or change? What would you keep?
- 3) How long did it take you to complete each app activity? How did this fit into your lifestyle and schedule?
- 4) At the completion of this study, would you want to keep using the MyPEEPS app? Why or why not?
- 5) Thinking back on the information you learned from the MyPEEPS app, how would you apply this information/lesson/activity in your own life? Have your health behaviors changed because of using the MyPEEPS app? If so, how/ what has changed in your health behaviors?

- 6) How do the MyPEEPS activities reflect your cultural beliefs, norms, and values and how were the MyPEEPS activities relevant or irrelevant to your sexual health or health overall?
- 7) How would you modify the outreach and enrollment to improve the process or make it easier?
- 8) How comfortable were you with the online recruitment and enrollment process?
- 9) Would you prefer the recruitment and enrollment process to be online or in-person? Please explain why.
- 10) Please describe what kind of access to HIV prevention information or care you have in your community or school? Do you feel like obtaining HIV prevention information is difficult for you? If so, please explain?

We will also ask probing questions to stimulate discussion. Furthermore, the guide will be informed by the feedback and commentary from members of our investigative team who have extensive clinical and research experience working with our study population. During the interview, the interviewer will also take notes.

Transcription: All individual interview audio recording will be transcribed verbatim through a transcription company. Any identifiers will be deleted from the audio and removed from the transcript. The team will adhere to qualitative processes to ensure the credibility, conformability, and dependability, and transferability of the qualitative data from these analyses. To support the credibility use “member checks,” i.e., sharing of initial data interpretations with participants, to ensure accurate interpretations. Triangulation of findings, along with reflexivity, will enhance the confirmability of the interpretations. The investigators will carefully record an audit trail and keep extensive field notes to facilitate transferability of study findings into other contexts (Guba, 1981). Transcripts will be analyzed independently for content by research team members in these methods.

Data Analysis: The research team will adhere to qualitative research processes to ensure the credibility, confirmability, dependability and transferability of the qualitative data from these analyses. The study team will meet and review transcripts and notes. Drs. [name] and [name]^{17,21,62-64} who both have experience in qualitative analysis will work with two research team members to code the transcripts. Field notes and transcripts will be analyzed by the researchers using NVivo™ (QSR International, Victoria, Australia) software. Participants' statements will be captured using memoing and then sorted into the categories of interest or descriptive thematic categories. Open coding will be used to develop initial data categories. Some codes will be derived from the questions included in the interview and other codes will emerge from themes and patterns identified in the narratives. An initial set of codes will be independently generated by two coders. Codes will then be compared and synthesized to result in shared coding categories and subcategories, all with definitions, inclusion and exclusion criteria, and examples. Coders will discuss discrepancies until they reach consensus. The research team will meet and review transcripts and notes. The goal is to collect feedback about the participants' overall experience with the MyPEEPS mobile RCT, technological difficulties, recruitment, and to identify subject matter that should be included to enhance the MyPEEPS mobile and recruitment process for future studies.

D. Assess the feasibility of using In-home HIV tests for assessing HIV status in a sample of very YMSM by conducting follow-up testing with MyPEEPS RCT participants.

Goals: Assess the feasibility of using the HIV home test for assessing HIV status in a sample of very YMSM.

Design Overview. In-home HIV testing will be conducted with MyPEEPS RCT participants 3 months following their completion of the trial. Participants will complete an in-home HIV test and an online survey that includes questions about demographic characteristics, health literacy, mental health and substance use, sexual risk behaviors, HIV testing history, and opinions regarding HIV testing.

Recruitment. We will recruit participants 3 months after they complete the MyPEEPS RCT. Participants will be contacted by study staff using their preferred method of communication to determine interest in the study. All participants within the recruitment timeframe (3 months post-RCT) will be approached except those withdrawn from the trial. Participants who voluntarily disclose to study staff while recruiting that they tested positive for HIV (seroconverted) when they were in the trial or since their participation ended will not be recruited in the current study but will be offered resources to be linked to care, if not already linked.

Sample. Our sample will include participants enrolled into the trial (inclusive of YMSM, Nonbinary individuals, and YTGW [who transitioned during or after the study], aged 13-21).

Eligibility criteria. In addition to being a MyPEEPS RCT participant, we will also include the following eligibility criteria: 1) understand the limitations of the OraQuick test (e.g., confirmatory test is needed); 2) not having tested positive for HIV since enrollment in the trial.

Study Enrollment. Study participants will conduct an enrollment visit remotely to provide informed consent (+17) or assent (13-16), enroll and complete provide an 'Address Survey' to provide a mailing address so study staff can send study materials needed for the baseline study visit. Remote informed consent will be conducted via video conferencing such as Skype, Zoom, FaceTime using REDCap to collect e-consent or e-assent and answer participant questions for the Address Survey. Through the REDCap platform, participants will be able to securely download a copy of the e-consent or e-assent for their records. As part of the REDCap e-consent/e-assent platform, the electronic forms will be automatically archived and securely stored in REDCap. Prior to the enrollment visit, those providing informed assent will be asked to have a parent or guardian provide e-consent to participate in the research. Parents/guardians will be able to provide e-consent through the REDCap platform and securely download a copy of the e-consent for their records. Those who secure parental/guardian consent will be asked in the Address Survey to confirm their parent/guardian's submitted consent and that they are aware of the materials that will be mailed to their home. All participants will complete an HIV Home Testing Understanding Assessment with study staff to ensure participants fully comprehend how to use the OraQuick rapid test prior to receiving it. Following enrollment, participants will be sent a study package with the following materials: an OraQuick in-home rapid HIV test kit, condoms, and study information listing the study team's contact information. OraQuick tests will be sent via tracked shipping through FedEx. During the remote baseline visit, participants will join via video conferencing to complete an in-home HIV test and an online survey that includes questions about demographic characteristics, health literacy, mental health and substance use, sexual risk behaviors including number of individuals they engaged in anal or oral sex with, condomless intercourse, as well as their HIV testing history, and opinions regarding HIV testing. The baseline survey will also include questions on PEP/PrEP use and adherence, drug and alcohol use, and the HIV Risk Index. The survey will also ask questions to assess the impacts of the COVID-19 outbreak. Remote participants who test negative (non-reactive) will receive the HIV prevention, PrEP assessment and referral information via a secure e-mail reviewed during the study visit video call. Remote participants who receive a preliminary positive result will be linked to care. Remote in-home HIV testing at baseline will use the OraQuick in-home tests. Participants will be shown how to conduct the test via video conference call. If a participant is found to be preliminary positive (reactive) during the baseline testing, they will be linked to care at a health clinic or hospital closest to them or a healthcare provider of their choice. If they are non-reactive, the study staff will wrap up the study visit. Study staff will record participant's HIV test results in their own individual REDCap record.

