The study population will consist of a diverse group of YMSM who live across the US. Each site will recruit an ethnically and racially diverse sample to include Blacks/African Americans, Hispanics/Latinos, American Indians/Alaska Natives, Asian Americans, Native Hawaiians and Other Pacific Islanders. We will also recruit "special populations" as described in our letters of support including: homeless youth and substance users. Race/ethnicity as well as these other special study populations (homeless or unstably housed, foster care, substance use) will be monitored throughout the study and recruitment will be adjusted and targeted with the intent of recruiting enough participants from each designated US health disparity population in sufficient numbers to conduct valid subgroup analyses.

C.5. Sample Size and Power Calculation.

We estimated the statistical power for the primary outcome of: number of condomless anal sex acts with male partners during the past 3 months (count outcome) based on the data from the MyPEEPS pilot study (R34MH079707). We estimated the statistical power for two scenarios: (1) to examine overall effect with total subjects; and (2) to conduct stratified analysis to examine the effects in some subgroups (such as by sex and/or for some racial/ethnicity subgroups). The following assumptions are used for the power estimation: (1) an 80% retention rate, at a single follow-up assessment for each

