study arm; (2) a conservative and high intra-cluster correlation (ICC) of 0.8, (3) mean number of unprotected anal sex acts with male partner partners with whom a condom was not used during the past 3 months at the baseline is 1.2,⁵ (4) all power estimations are based on $\alpha=0.05$ and 2-sided tests. Findings from our MyPEEPS pilot study indicate that the post-intervention number of condomless anal sex acts during the past 6 weeks decreased by 63%, or a relative risk (RR) of 0.37.⁵ However, the large effect was not statistically significant. Because the estimated effect size of the intervention was unreliable, instead, we use RR=0.73, one standard error over the estimated RR of 0.37, as the effect size for the examination of overall effect of intervention for total sample. This would provide a conservative estimation of minimum sample size need. For the subgroup analyses, we use the effect size of RR=0.37. To examine overall effect with total subjects, we expect that the post-intervention number of unprotected anal sex acts 27% (i.e., RR=0.73). We will have 97% power to detect such difference for the total sample size of 700. To test absolute relative difference (the equivalent margin) of <10% for the outcome with n=700. Secondly, for the stratified analyses, we will have 92% power to detect a relative risk of 0.37 in subgroups with sample size of 70. As per the RFA, we will have adequately powered comparisons that can be done separately for racial/ethnic groups, age (by year), geographic region (Northeast, South, Midwest and West), and socioeconomic status. In order to achieve this, each subgroup will need to have about 10% of the total subjects. For example, we anticipate recruiting 70 American Indians across all sites so that we will have enough power to detect a significant effect of the MyPEEPS Mobile intervention (See Planned Enrollment Table). To test whether the intervention is effective during the follow-up period, we will have 61% power to detect an absolute relative difference (the equivalent margin) of <10% or 95% power to detect an absolute relative difference of <15% for the outcome with n=70. However, we will increase target enrollment to n=900 to provide a better possibility of reaching the above indicated sample sizes for each subgroup.

C.6. Sampling Approach.

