Contact (phone calls, text, email or note as preferred by the participant) will be made by the site study staff prior to the follow-up visit to confirm or reschedule an appointment. The discrete contact will thank the participants for being in the program, remind them of the date and time of their next follow-up appointment and note the telephone number that can be called if rescheduling is necessary. Participants who do not respond and cannot be located during the acceptable window period are coded as a missed assessment and contact will continue for the next assessment. We will contact participant until they expresses the desire to be dropped from the study. If a participant moves away from the original project conducted or arrangements will be made to transfer their contact information to a different site. These extensive procedures will be used to promote participant attendance at the follow-up visits and has been shown to be successful in previous intervention trials.¹⁰² Using the following sound retention efforts as well as reimbursement for completion of surveys, we are confident that we will retain at least 80% of our study sample at a single follow-up assessment for each study arm.⁸⁶ We have methods in place to maximize intervention completion including: 1) gaming components of our intervention, 2) monetary compensation for completion of intervention modules, and 3) automated electronic (e-mail/ text) reminders.

C.14. Statistical Procedures:

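### The only missing-data sensitivity analysis does not relax missing at random, so agreement between its two arms of comparison cannot show that attrition leaves the result unaffected

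*Combined protocol and SAP*

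**What the plan says.** Section C.14 relies on the mixed model (GLMM) for missing follow-up outcomes: "One of the main advantages of GLMM is to provide unbiased estimates when there are missing outcomes during the follow up period". It attaches no condition to that claim. Multiple imputation is specified there for missing or partial baseline data, and the models are also to be run without imputation. C.14 then states that inferences for arm, wave and the "interaction between trial arm and wave did not differ between the analyses of the raw and multiply imputed data".

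C.14.a adds prorating for item non-response and a review of the amount, reasons and patterns of missing data. If the reason is unrelated to the outcome, the "missing data are considered to be missing completely at random (MCAR) and complete case analysis will still generate unbiased estimates". The one sensitivity analysis is to "compare estimates of treatment effects with and without multiple imputation to assess the effect of missing data on statistical inference".

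On the expected loss, C.13 is confident that the study will "retain at least 80% of our study sample at a single follow-up assessment for each study arm", and C.5 assumes the same 80% for power. No section plans an analysis in which missing outcomes differ systematically from what the observed data predict.

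**The concern.** A likelihood mixed model on available data is valid when missingness depends only on observed data. Standard multiple imputation needs the same condition. If the non-imputed run drops people with incomplete baseline covariates, it needs something stronger. Neither analysis asks what happens if those lost behaved differently from those with the same recorded history, so comparing them does not test the assumption on which both rest. Because only baseline data are named for imputation, the two runs may also treat missing follow-up outcomes identically.

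The assumption deserves a test here. The outcome is self-reported sexual risk, and participants know whether they have the app. The delayed arm waits 9 months for access (C.8.3), and module payments can reach $100 (C.13). Loss related to behaviour, and related differently by arm, is plausible, though the documents do not say in which direction. The risk is that agreement between the two runs is reported as robustness. The past-tense sentence invites this, because it gives the result of a comparison that has not been run.

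**Working it through.** **Inputs from the documents.** Power assumptions (C.5): "all power estimations are based on $\alpha=0.05$ and 2-sided tests"; retention is "an 80% retention rate, at a single follow-up assessment for each" arm; the mean count of condomless anal sex acts "during the past 3 months at the baseline is 1.2"; RR 0.73; total 700, with enrolment raised to 900. Equal allocation is an assumption, since no ratio is stated.

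**The plan's own figure.** The missing-data plan gives no figure, so the check starts from the power figure that carries the retention assumption. Two-group Poisson test on log RR:

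- SE² = 1/(n × 1.2) + 1/(n × 1.2 × RR); power = Φ(|ln RR|/SE − 1.96).
- n = 700 × 0.8 / 2 = 280 per arm: SE = 0.0840, power 96.3%.
- n = 350 per arm (no loss): SE = 0.0751, power 98.7%.

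Both lie within two points of the stated 97%, so this simple test is a fair scale for the illustration.

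**Only intervention-arm dropouts depart.** Assume 20% missing per arm, observed RR 0.73, missing controls like observed controls, and missing intervention participants at k times the control rate. Then RR = 0.8 × 0.73 + 0.2 × k, with SE recomputed at the new RR. For 900 enrolled, 900 × 0.8 / 2 = 360 retained per arm.

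| k | RR | z, n = 280 | z, n = 360 |
|---|---|---|---|
| 1.0 | 0.784 | −2.96 | −3.35 |
| 1.25 | 0.834 | −2.24 | −2.54 |
| 1.5 | 0.884 | −1.55 | −1.76 |
| 2.0 | 0.984 | −0.21 | −0.24 |

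Significance is lost at k of about 1.35 (n = 280) to 1.43 (n = 360). With 450 per arm, z at k = 1.5 is −1.96, which is borderline.

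C.14 also allows a negative binomial model but gives no dispersion. Adding an assumed dispersion κ to each arm's variance (SE² gains 2κ/n), the crossing point at n = 360 is about 1.28, 1.16 and 0.97 times the control rate for κ = 0.5, 1 and 2.

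**Dropouts in both arms worsen equally.** If dropouts in both arms are at k times the observed control rate, RR = (0.584 + 0.2k)/(0.8 + 0.2k), and the control mean becomes 1.2 × (0.8 + 0.2k).

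- k = 1.5: RR = 0.884/1.10 = 0.804; z = −2.81 (n = 280) to −3.18 (n = 360).
- k = 2: RR = 0.984/1.20 = 0.820; z = −2.67 to −3.03.

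Significance is kept in both cases.

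**Can the planned comparison miss a false effect?** This was tested in 600 simulated trials of 900 participants with true RR 1.0 and negative binomial counts (mean 1.2, dispersion 1). Controls were lost at random (20%). Intervention participants were lost with probability 0.46 if their unseen follow-up count was 2 or more, and 0.08 otherwise. Average loss was 19.4% in the intervention arm and 20.0% in the control arm.

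| Analysis | RR | Rejections |
|---|---|---|
| Complete data | 0.996 | 4.8% |
| Available data | 0.811 | 61% |
| Multiple imputation | 0.810 | 58% |

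The last two agreed on significance in 93% of runs and differed by 0.012 on the log scale on average. Here the follow-up counts themselves were imputed, which is more than the plan specifies. The model was a single-follow-up regression adjusted for baseline, not the full GLMM. It shows what can happen under one constructed mechanism and predicts nothing about this trial.

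**The case against.** Several points on the other side stand.

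- A reader might infer that the imputed and non-imputed analyses must agree by construction. The documents do not support this. Imputation is specified for baseline data, and a non-imputed run may drop people with incomplete baselines, so the two could differ. What remains is that agreement would not test missing at random.
- A reader might infer that the plan adopts complete-case analysis under MCAR. It does not. The sentence is conditional and the planned analysis is the GLMM. The remaining weakness is that inspecting reasons and patterns cannot establish MCAR.
- The arm-by-wave interaction is not wholly foreign to the model. No such term is written, but Table 4 makes the indicator I depend on both arm and wave, so it partly plays that role.
- The illustration is one-sided: it turns non-significant under Poisson variance only when intervention-arm dropouts alone do materially worse than controls. It is a single-wave test, not the repeated-measures parameter β3.
- Twenty percent is a planning ceiling at one follow-up.
- The plan limits the problem in other ways. Collection continues after a missed visit (C.9, C.13), remote assessment is offered to those who move (C.3), and covariates may make missing at random more credible (C.14).

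These measures reduce the likely bias. None of them tests for it.

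**Conclusion.** The plan makes an unconditional claim of unbiasedness, offers a single check that cannot challenge the assumption behind that claim, and records the outcome of the check in advance. The imputation scope leaves it unclear whether missing follow-up outcomes are examined at all.

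A reader might go further and infer that 20% attrition would overturn the result. The documents do not support that. Under the stated Poisson illustration, the finding survives intervention-arm dropouts at the control rate (RR 0.78) and at 1.25 times it (0.83), and survives equal worsening in both arms (RR 0.80 to 0.82). It becomes non-significant near 1.35 to 1.43 times the control rate when only the intervention arm departs; at 1.5 times, RR is 0.88 and |z| 1.55 to 1.76 with 280 to 360 retained per arm. Greater dispersion would bring that point closer, by an amount the documents do not allow one to fix. The answer depends on who is lost, and the planned comparison would not reveal it. This should be corrected, but it does not invalidate the primary model.

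**What to change.** 1. In C.14, state that the GLMM estimate is valid under missing at random given the modelled data.
2. Delete the past-tense sentence reporting that inferences agreed.
3. State whether follow-up outcomes, or only baseline data, are imputed in the comparison in C.14.a.
4. Add one pre-specified sensitivity analysis for the count used in the power calculation, condomless anal sex acts. Impute missing intervention-arm follow-up counts at the control-arm rate, then apply a pre-specified range of multipliers varied in each arm, and report the tipping point. The trial team should justify the range before outcomes by arm are seen; the documents offer no basis for particular values.
5. Reword the MCAR sentence so that a review of reasons and patterns is described as descriptive and not as establishing MCAR.

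The cost is SAP wording and modest extra analysis work. No new data are needed.
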